8.3 Study Visits or Study Assessments

8.3.1 Day -5 (IS Reduction Arm)

Participants randomized to the IS reduction arm will have a Day -5 visit. A study physician will discuss what IS medication will be withheld or reduced based on the participant's IS regimen at study entry (see Section 6.3 for further details).

8.3.2 Vaccination Visit: Day 0 (All Participants)

All participants will be scheduled for a vaccination visit.

Participants will have baseline research blood, oral fluid, and nasal samples collected on Day 0 per the Schedule of Events (Appendix 2 (COVID-19 Vaccine Dose Alone) and Appendix 3 (IS Reduction plus COVID-19 Vaccine Dose)). Following sample collection, the participant will proceed to the administration location and receive the assigned dose of COVID-19 vaccine (see [Section 6](#) for vaccine details).

Participants will be observed for 30 minutes post vaccine administration.

8.3.3 Follow-up Visits (All Participants)

Follow-up will occur at weeks 1, 2, 3, 4, 5, 6 and Months 3, 6, 9, and 12 following vaccine administration. Participants will have additional blood tests to monitor their graft function during the time they are on a reduced level of immunosuppression and for 1 month following resumption of their original regimen of immunosuppression. Identical blood testing schedules will take place for both the COVID-19 vaccine dose group and the IS reduction plus COVID-19 vaccine dose group. Kidney recipients will have their serum creatinine levels measured at the weekly visits. Liver recipients will have a hepatic panel (AST, ALT, alk phos, bilirubin, direct bilirubin) at the weekly visits.

The Week 4 visit is the primary endpoint visit. During these visits, participants will be asked about their general health, any new events, immunosuppression medications and their transplanted organ per the Schedule of Events in Appendix 2.

Blood and nasal swabs will be collected for assessments to be run in the clinical and research laboratories per the Schedule of Events in Appendix 2 or Appendix 3 based on group assignment. Nasal mid-turbinate swabs for SARS-CoV-2 PCR testing will be collected at baseline and Months 1, 3, 6, 9 and 12 following vaccine administration.

Participants will be instructed to contact the study team if they receive any COVID-19 testing at an outside lab during the course of the study. All instances of COVID-19 infection will be reported on the applicable electronic case report form.

A subset of participants will have a study visit on Day 3 to have blood drawn for a research laboratory study to detect the presence of SARS-CoV-2 spike protein generated in response to the vaccine.

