Acute Myocarditis / Acute Pericarditis	Myocarditis is inflammation of the heart muscle. Pericarditis is inflammation of the lining outside the heart. In this study, the definition of suspected or confirmed acute myocarditis or acute pericarditis is the Centers for Disease Control and Prevention (CDC) case definition criteria: https://www.cdc.gov/mmwr/volumes/70/wr/mm7027e2.htm
Basic Metabolic Panel	Includes sodium, potassium, chloride, carbon dioxide (CO ₂) total, blood urea nitrogen, creatinine, glucose, calcium, anion gap and BUN/creatinine ratio.
Comprehensive Metabolic Panel	Includes sodium, potassium, chloride, carbon dioxide (CO ₂) total, blood urea nitrogen, creatinine, glucose, calcium, total protein, albumin, total bilirubin, alkaline phosphatase (Alk Phos), aspartate aminotransferase (AST), alanine aminotransferase (ALT), anion gap, BUN/creatinine ratio, and AST/ALT ratio.
Donor Specific Antibodies (DSA)	Antibodies directed at donor human leukocyte antigens (HLA) by central lab assessment.
Graft Failure	
Kidney: Any of the following events: renal dialysis of more than 3 months duration; listing for re-transplantation; death from kidney failure.
 
Liver: Re-listing for transplantation or death from liver failure.

IS Reduction Failure	Participant resumes baseline IS per the criteria outlined in Section 6.7 Premature Discontinuation of IS Reduction but does not receive definitive treatment for rejection e.g. thymoglobulin, steroids, or a sustained increase in dose or number of immunosuppressive medications.
Lost to Follow-up	Missing primary endpoint assessment and/or final study visit.
Medical Monitor	The physician who is responsible for Sponsor oversight of safety aspects of the trial. The medical monitor will determine the attribution of Serious Adverse Events after considering all investigator input.
Significant Graft Dysfunction for Study Eligibility	
Kidney: eGFR <35mL/min/1.73m².
 
Liver: INR >ULN (in patients not on anticoagulation), direct bilirubin >1.

Negative or indeterminate Antibody Titer	A measurement of <0.8 U/mL using the Roche Elecsys® anti-SARS-CoV-2 S assay.

NIAID Project Manager	NIAID assigned project manager who is responsible for all day to day administrative protocol-related issues, including version control, consent review, etc.

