6.7 Immunosuppression Reduction

6.7.1 Immunosuppression (IS) Reduction

Participants on a tacrolimus-based regimen that includes MMF (or equivalent), with or without corticosteroid:

MMF (or equivalent) will be withheld for five days prior to and 2 weeks following vaccine administration. During the interval that MMF is withheld, no adjustments will be made to the CNI or corticosteroid dose.

Participants on a tacrolimus based regimen with a trough level ≥ 5 ng/mL, with or without ≤ 5 mg Prednisone (or equivalent) and no MMF or other antimetabolite

Reduce CNI by 25% of starting dose for 5 days prior to and 2 weeks following vaccine administration.

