6.12 Premature Discontinuation of IS Reduction

Monitoring for evidence of rejection during IS reduction is described in Section 8.3.3. A persistent increase in creatinine (for kidney recipients) or of ALT (for liver recipients) will be cause for return to baseline IS, as follows:

For kidney transplant recipients: A finding of a 0.3mg/dL or 25% elevation (whichever is higher) of serum creatinine over baseline (pre-reduction in IS) will be repeated in 1-3 days. If the elevation persists or increases, the subject will return to his/her baseline immunosuppression regimen. Further management will be determined by the treating transplant physician. If the serum creatinine returns to baseline without further treatment, the event will not be recorded as rejection. If the participant requires more than baseline levels of IS or receives specific treatment for rejection, the event will be recorded as rejection.

For liver transplant recipients: A finding of an elevation of an ALT >2X baseline (pre-reduction in IS) or >60 IU/L if the baseline ALT is <30 IU/L will be repeated in 1-3 days. If the elevation persists or increases, the subject will return to his/her baseline immunosuppression regimen. Further management will be determined by the treating transplant physician. If the ALT returns to baseline without further treatment,

the event will not be recorded as rejection. If the participant requires more than baseline levels of IS or receives specific treatment for rejection, the event will be recorded as rejection.

7. Other Medications

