Appendix 2: Schedule of Events (COVID-19 Vaccine Dose Alone)

Study Schedule	Days		Weeks						Months				
Time points	0	3 ¹	1	2	3	4	5	6	3	6	9	12	For Cause ²
Visit #	01	02	03	04	05	06	07	08	09	10	11	12	FC
Visit Windows (+/-)	-	1d	1d	3d	3d	3d	3d	3d	2w	2w	2w	2w	-
General Assessments													
Study Contact ³	X		X	X	X	X	X	X	X	X		X	X
Medications (immunosuppression, PrEP, COVID-19 treatment)	X ⁴	→	→	→	→	→	→	→	X	X ⁵	X ⁵	X ⁵	X
Assessment of Events (AE, SAE, rejection, graft loss)	X	→	→	→	→	→	→	→	→	→	→	X	X
Clinical Laboratory Assessments													
Complete Blood Count with differential	X			X		X			X	X		X	
Metabolic Panel ⁶	X								X	X		X	
eGFR, serum creatinine (kidney)	X		X	X	X	X	X	X					
Hepatic Panel including direct bilirubin (liver)	X									X			
Quantitative Immunoglobulins	X									X			
SARS-CoV-2 PCR (nasal swab, clinical)	X ⁷					X			X	X	X	X	X
Investigational Intervention													
COVID-19 mRNA Vaccine	X												
Central Laboratory Assessments													
SARS-CoV-2 PCR (nasal swab, research)	X					X			X	X		X	X
Oral fluid anti-N and anti-S immunoglobulin levels	X					X			X	X		X	X
Anti-SARS-CoV-2 S (Roche Elecsys®)				X		X			X	X		X	X
Donor Specific Antibodies (kidney only)						X			X	X		X	X
Antibody/Neutralization assays	X			X		X			X	X		X	X
Spike Protein (subset of sites)	X	X											
Proteomics	X	X ⁸				X							
Transcriptomics	X	X ⁷				X							
T and B Cell Assays	X			X		X			X	X		X	X

¹ May be a home draw. The spike protein will only be performed at a subset of clinical sites.

² Unscheduled "for cause" visit for suspected rejection. Participants with confirmed COVID-19 will send in a nasal swab for research.

³ Study contacts may be remote.

⁴ Ensure the participant has not taken any medications since screening that would make them ineligible.

⁵ Only PrEP and COVID-19 related treatment collected at these visits.

⁶ Comprehensive metabolic panel at baseline, basic metabolic panel all other timepoints (see study definitions).

⁷ If the Day 0 nasal swab is positive, the participant will be prematurely discontinued and followed until Day 30 for safety. This includes the Day 30 clinical labs, DSA and AE/SAE assessment. No further mechanistic blood will be collected.

⁸ These Day 3 assessments will only be collected on participants included in the Day 3 spike protein.

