Appendix 3: Schedule of Events (IS Reduction plus COVID-19 Vaccine Dose)

Study Schedule	Days			Weeks						Months				
Time points	-5	0	3 ¹	1	2	3	4	5	6	3	6	9	12	For Cause ²
Visit #	01	02	03	04	05	06	07	08	09	10	11	12	13	FC
Visit Windows (+/-)	-	-	1d	1d	3d	3d	3d	3d	3d	2w	2w	2w	2w	-
General Assessments														
Study Contact ³	X	X		X	X	X	X	X	X	X	X		X	X
Medications (immunosuppression, PrEP, COVID-19 treatment)	X ⁴	→	→	→	→	→	→	→	→	X	X ⁵	X ⁵	X ⁵	X
Assessment of Events (AE, SAE, rejection, graft loss)	X	→	→	→	→	→	→	→	→	→	→	→	X	X
Clinical Laboratory Assessments														
Complete Blood Count with differential		X			X		X				X	X		X
Metabolic Panel ⁶		X								X	X			X
eGFR, serum creatinine (kidney)		X		X	X	X	X	X	X					
Hepatic Panel including direct bilirubin (liver)		X									X			
Quantitative Immunoglobulins		X									X			
SARS-CoV-2 PCR (nasal swab, clinical)		X ⁷					X			X	X	X	X	X
Investigational Intervention														
Immunosuppression Reduction	X	→	→	→	X ⁸									
COVID-19 mRNA Vaccine		X												
Central Laboratory Assessments														
SARS-CoV-2 PCR (nasal swab, research)		X					X			X	X		X	X
Oral fluid anti-N and anti-S immunoglobulin levels		X					X			X	X		X	X
Anti-SARS-CoV-2 S (Roche Elecsys [®])					X		X			X	X		X	X
Donor Specific Antibodies (kidney only)							X			X	X		X	
Antibody/Neutralization assays		X			X		X			X	X		X	X
Spike Protein (subset of sites)		X	X											
Proteomics		X	X ⁹				X							
Transcriptomics		X	X ⁸				X							
T and B Cell Assays		X			X		X			X	X		X	X

¹ May be a home draw. The spike protein will only be performed at a subset of clinical sites.² Unscheduled "for cause" visit for suspected rejection. Participants with confirmed COVID-19 will send in a nasal swab for research.³ Study contacts may be remote.⁴ Ensure the participant has not taken any medications since screening that would make them ineligible.⁵ Only PrEP and COVID-19 related treatment collected at these visits.⁶ Comprehensive metabolic panel at baseline, basic metabolic panel all other timepoints (see study definitions).⁷ If the Day 0 nasal swab is positive, IS reduction will be prematurely discontinued and participants will be followed until Day 30 for safety. This includes the Day 30 clinical labs, DSA and AE/SAE assessment. No further mechanistic blood will be collected.⁸ Participant will be informed to restart full IS the following day.⁹ These Day 3 assessments will only be collected on participants included in the Day 3 spike protein.

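### Section 8.3.3 requires a weekly hepatic panel in liver recipients, but the schedules in Appendices 2 and 3 mark it only at Day 0 and Month 6, so they schedule no ALT in Weeks 1-6

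*Combined protocol and SAP*

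**What the plan says.** Section 8.3.3 sets follow-up visits at Weeks 1 to 6 and Months 3, 6, 9 and 12. It calls for graft-function blood tests throughout the reduction and for one month after full immunosuppression resumes, on the same schedule in both arms. Kidney recipients have creatinine at each weekly visit. For liver recipients the text is equally direct: "Liver recipients will have a hepatic panel (AST, ALT, alk phos, bilirubin, direct bilirubin) at the weekly visits".

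The same section then says that samples are collected for assessments "run in the clinical and research laboratories per the Schedule of Events in Appendix 2 or Appendix 3 based on group assignment". In both appendices the hepatic panel row carries two marks, at Day 0 and Month 6.

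Section 6.12 holds the rule that depends on these tests. It opens "Monitoring for evidence of rejection during IS reduction is described in Section 8.3.3". For liver recipients the trigger is "A finding of an elevation of an ALT >2X baseline (pre-reduction in IS) or >60 IU/L if the baseline ALT is <30 IU/L". The value is repeated in 1 to 3 days, and if the rise persists the participant goes back to the baseline regimen.

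Section 6.7.1 gives the period at risk: "MMF (or equivalent) will be withheld for five days prior to and 2 weeks following vaccine administration". The tacrolimus reduction in participants without an antimetabolite covers the same interval.

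**The concern.** The text and the schedule give sites two different instructions for the same test, and nothing in the protocol says which prevails. A coordinator working from the appendix, to which Section 8.3.3 itself points, would order no ALT between Day 0 and Month 6. A coordinator working from the narrative would order six.

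The liver arm of the Section 6.12 rule starts from a first raised ALT. After Day 0, a site following the appendix would obtain that value only from unscheduled or for-cause testing. Section 5.3 relies on close monitoring for graft injury during the reduction to justify its risk. Treated rejection within 60 days is a secondary safety endpoint, and the rejection pausing rule in Section 11.5 counts events by group. If sites differ in how often they look, ALT-based detection of liver graft injury differs with them.

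**Working it through.** There is no plan figure to reproduce. The check compares scheduled marks by row and looks for any other source of ALT.

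**1. Marks by row, read against the time-point header (13 columns in Appendix 2, 14 in Appendix 3).**

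| Row | Appendix 2 | Appendix 3 | Section 8.3.3 text, weekly visits |
|---|---|---|---|
| Creatinine/eGFR (kidney) | Day 0, Weeks 1-6 (7 marks) | Day 0, Weeks 1-6 (7 marks) | Weeks 1-6 |
| Hepatic panel (liver) | Day 0, Month 6 (2 marks) | Day 0, Month 6 (2 marks) | Weeks 1-6 |
| Metabolic panel | Day 0, Months 3, 6, 12 (4 marks) | 4 marks, none in Weeks 1-6 | not mentioned |

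The kidney half of Section 8.3.3 reached the schedule; the liver half did not.

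**2. Other sources of ALT.** Footnote 6 of both appendices makes the metabolic panel comprehensive (with ALT) at baseline only and basic afterwards. The Study Definitions list for the basic panel ends "glucose, calcium, anion gap and BUN/creatinine ratio" and contains no liver enzyme. The hepatic panel row is also blank in the For Cause column. Donor-specific antibody is scheduled for kidney recipients only. For liver recipients the hepatic panel is therefore the only scheduled laboratory check on graft injury.

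**3. Size of the gap if a site follows the appendix.**
- Day 0 to Week 6: 1 of 7 for liver ALT, 7 of 7 for kidney creatinine.
- On reduction in the reduction arm (Day 0, Week 1, Week 2): 1 of 3.
- After resumption (Weeks 3-6): 0 of 4.
- Reduction runs from Day -5 to Day 14, which is 5 + 14 = 19 days. The share after the Day 0 test is 14/19 = 74%.
- The rest of the 60-day rejection window has no scheduled ALT either. The next mark is Month 6, about Day 183; with the 2-week window, 183 - 14 = 169 to 183 + 14 = 197.

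A pre-reduction baseline does exist, because Section 8.2 requires a hepatic panel at screening. What is missing is the later values to compare with it.

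**4. Size of the gap if a site follows Section 8.3.3.** None: six weekly panels are drawn in Weeks 1-6.

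**5. Could this be a PDF-reading error?** Some marks in Appendix 3 are displaced: the last metabolic panel mark reads under For Cause, where Appendix 2 has Month 12. A displacement moves marks along a row. It does not turn a weekly series into no weekly marks, and both tables show the same two marks while the nearby creatinine row is intact. A misread of the whole row is not excluded, because the Quantitative Immunoglobulins row directly below shows the same Day 0 and Month 6 pattern.

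**The case against.** The strongest reply is that the protocol does schedule the ALT, in Section 8.3.3, and that Section 6.12 cites that section and not the appendices. On this reading the pointer to the appendices is general and cannot cancel the specific hepatic-panel sentence beside it. The counts above apply only to a site that follows the table and disregards the text, and the documents do not show that any site does. That condition is accepted: the defect is a conflict between text and schedule, not an absence of monitoring. It still needs resolving, because the schedule is where Section 8.3.3 sends sites and no order of precedence is given.

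A second reply concerns the extraction. Besides the displaced marks, the donor-specific antibody row has a For Cause mark in Appendix 2 and none in Appendix 3. That could be a lost mark. Both tables were also read by the same program, so their agreement is not fully independent. This justifies looking at the source PDF first. It does not make the loss of six marks from the same row in two tables a likely explanation.

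A third reply is that little is lost. Assessment of rejection and graft loss runs throughout, unscheduled and for-cause visits exist, and the primary endpoint is untouched. This is right, and it limits the severity.

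Finally, the correction is not free. For liver recipients, Weeks 1, 3, 5 and 6 carry no other marked blood draw, and footnote 3 allows remote contacts. A site that had followed the appendix would add four draws per liver recipient at visits that otherwise need none. Section 8.3.3 already requires those draws, so they are not a new burden under the protocol as written.

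**Conclusion.** The concern holds. Taken at face value, Appendices 2 and 3 contradict Section 8.3.3 and leave the ALT rule in Section 6.12 without a scheduled test after Day 0. For a site following the appendix, scheduled ALT falls from 6 to 0 over Weeks 1-6, and 14 of 19 reduction days (74%) in the reduction arm are uncovered. For a site following the text there is no gap. Which practice sites follow cannot be known from the documents. Nor can the direction or size of any effect on the comparison of rejection between arms, because no kidney/liver split is given and both arms' tables carry the same omission. The conclusion assumes that the extracted rows reflect the original tables. It should be fixed because it concerns the scheduled laboratory safeguard for liver grafts during a deliberate reduction of immunosuppression.

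**What to change.** Check the hepatic panel row in the source PDF of both appendices. If it reads as extracted, mark the panel at Weeks 1, 2, 3, 4, 5 and 6 in Appendix 2 and Appendix 3, identically in both arms, to match Section 8.3.3 and the creatinine row.

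The edit is one row in each of two tables, with the sponsor and IRB approval that Section 17.1 requires for an amendment. It adds no test beyond those Section 8.3.3 already prescribes, and the weekly visits are already planned. At sites that have been using the appendix, the weekly contacts for liver recipients will have to include a blood draw. Randomisation, endpoints and analysis do not change.

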8.4 Unscheduled Visits

If there is a change in immunosuppressive medications, new medical events or a diagnosis of rejection between regularly scheduled visits, participants will be instructed to contact study personnel and may be asked to return to the study site for an “unscheduled” visit.

8.5 Suspected or Confirmed Myocarditis or Pericarditis

Participants will be instructed to seek prompt medical attention if they develop symptoms of myocarditis or pericarditis, such as including chest pain, shortness of breath, or palpitations. Participants will also be instructed to notify the study site team. Participants diagnosed with acute myocarditis or acute pericarditis within 6 weeks of any COVID-19 vaccine will be referred to a cardiologist for evaluation and management.

Cases of study-defined probable or definite acute myocarditis or acute pericarditis will be followed until resolution of symptoms and abnormal test findings.

8.6 Suspected or Confirmed Cases of COVID-19 Infection

If participants suspect they have contracted COVID-19 infection, they will be directed to follow-up with their local transplant physician or primary care provider to obtain the appropriate clinical care. Information related to their illness will be collected for the study and reported in the clinical database.

8.7 Visit Windows

Study visits should take place within the time limits specified below: the designated visit windows (*i.e.* +/- *n* days) for each scheduled visit are also indicated on the Table of Events.

Screening	-30 days for screening clinical laboratory assessments SARS-CoV-2 S antibody at least 30 days following last dose of COVID-19 vaccine -90 days for dnDSA
Day 3, Week 1	+/- 1 day
Weeks 2, 3, 4, 5, and 6	+/- 3 days
Months 3, 6, 9, and 12	+/- 2 weeks

9. Mechanistic Assays

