3.3 Secondary Endpoints

3.3.1 Secondary Safety Endpoints

Local and systemic vaccine reactogenicity and/or allergy
Serious adverse events occurring during the 30 days following the additional dose of vaccine
Treated acute cell-mediated and/or antibody-mediated allograft rejection (clinical or biopsy-proven) within 60 days following the additional dose of vaccine
Development of de novo donor-specific anti-HLA antibody within 90 days of the vaccine
Graft loss within 60 days of the vaccine
Death within 60 days of the vaccine

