4.2 Inclusion Criteria

Individuals who meet all the following criteria are eligible for enrollment as study participants:

1. Able to understand and provide informed consent.
2. Individual ≥ 18 years of age.
3. Recipient of a kidney or liver transplant ≥ 12 months prior to enrollment, without allograft rejection in the 6 months preceding enrollment.
4. Negative for anti-donor HLA antibodies at screening (central lab).
5. Currently taking one of the following CNJ-based immunosuppressive regimens:
 - Tacrolimus plus MMF or MPA, with or without a corticosteroid
 - Tacrolimus with trough ≥ 5 ng/mL with or without ≤ 5 mg of prednisone or equivalent
6. Received a minimum of 3 doses of either the Moderna COVID-19 Vaccine or Pfizer-BioNTech COVID-19 Vaccine.
7. Participant must be ≥ 60 days after completion of primary vaccination or receipt of the most recent booster dose with any authorized or approved monovalent or bivalent COVID-19 vaccine at the time of study vaccine.
8. Serum antibody negative or low (titer ≤ 2500 U/mL) at ≥ 30 days from the last dose of mRNA COVID-19 vaccine and ≥ 30 days following receipt of a monoclonal antibody product or convalescent plasma for COVID-19, measured using the Roche Elecsys® anti-SARS-CoV-2 S assay.
9. Participant's transplant physician or midlevel practitioner who is clinically licensed to prescribe and manage immunosuppression must confirm the participant's eligibility based on medical history.

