13.5.2 Interim Analysis of Safety Data

Excess incidence of dnDSA in kidney transplant recipients: An interim analysis will be performed to look for evidence of an excess incidence of dnDSA in the IS reduction groups (those undergoing withdrawal of MMF; and those undergoing a decrease in CNI dose) as compared with those receiving an additional dose of vaccine alone. When fifteen subjects in each of these groups have reached day 30 in the study (study visit 4), the core HLA lab will determine whether de novo DSA is present. We will perform a similar analysis when fifty subjects in each group have reached day 30. At each of these two time points, the proportion with Class II dnDSA in each IS reduction group will be compared with the COVID-19 vaccine dose alone group using a one-sided Fisher exact test to determine if there is an excess incidence of Class II dnDSA, and the results presented to the DSMB for review

[figure not shown]

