Appendix 1: Screening (All Participants)

Initial Screening Assessment

• Chart review• Antibody consent• Anti-SARS-CoV-2 S (Roche Assay)
Final Screen

• Study consent form• Serum creatinine, eGFR (Kidney)• DSA (kidney only, sent to central lab, 90 day window)• Research blood (sent to central lab)• Hepatic panel, INR, direct bilirubin (liver)• Tacrolimus trough level• Pregnancy test (women of childbearing potential)
Randomization

1) Once the participant meets full eligibility, the participant may be randomized2) Once the participant is randomized, the appropriate appendix should be followed based on the group assignment:
○ Appendix 2: COVID-19 Vaccine Dose Alone 
OR
 
○ Appendix 3: IS Reduction plus COVID-19 Vaccine Dose

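### Donor-specific antibody (DSA) present before the intervention is counted as de novo in both arms, because the qualifying negative test may be 90 days old and is not repeated at Day -5 or Day 0

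*Combined protocol and SAP*

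**What the plan says.** Eligibility requires a negative central-lab result at screening: "Negative for anti-donor HLA antibodies at screening (central lab" (section 4.2). Section 8.7 allows "90 days for dnDSA", against "30 days for screening clinical laboratory assessments" for the other laboratory tests. Appendix 1 repeats the limit: "DSA (kidney only, sent to central lab, 90 day window". Neither place says whether the 90 days run back from Day 0, Day -5 or randomization.

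The row "Donor Specific Antibodies (kidney only" in Appendix 2, and its counterpart in Appendix 3, start at Week 4 and continue at Months 3, 6 and 12. Neither has a mark at Day 0, and Appendix 3 has none at Day -5. The Study Definitions page defines DSA but not de novo, and names no reference sample.

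Two analyses use the result. Section 3.3.1 lists "Development of de novo donor-specific anti-HLA antibody within 90 days of the vaccine" as a secondary safety endpoint; section 13.4.3 tests it with Fisher's exact test. Section 13.5.2 adds interim looks at 15 and 50 kidney recipients per group, for which the central laboratory classifies each person's DSA status: "When fifteen subjects in each of these groups have reached day 30 in the study (study visit 4), the core HLA lab will determine". Class II proportions are then compared with vaccine alone by a one-sided Fisher test. (Visit 4 is not Week 4 in either appendix. I read day 30 as the Week 4 visit, the first with a DSA mark.)

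Blood is available before vaccination in both arms: "Participants will have baseline research blood, oral fluid, and nasal samples collected on Day 0 per the Schedule of Events" (section 8.3.2). No DSA test on it is planned.

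**The concern.** With no other reference sample named, the screening result is the only baseline. A kidney recipient who converts after screening but before the intervention enters as negative, tests positive at Week 4 and is scored as de novo within 90 days of the vaccine. The same person counts in the Day 30 interim comparison. Neither reduction nor vaccine can have caused that event.

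This matters because section 2.1 hypothesizes a better response without more alloimmune events, while section 13.6 sets every test as superiority. A non-significant DSA comparison is therefore likely to be read as reassurance, and unrelated background events make non-significance more likely when there is a true excess. The interim looks are small enough for one such event to change the result. For an individual Week 4 positive, the DSMB cannot tell whether the antibody preceded the intervention.

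**Working it through.** The plan gives no DSA rate, target excess or power, so there is no stated figure to reproduce.

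**Inputs from the documents.** Screening sample up to 90 days old (8.7, Appendix 1); first tests at Week 4 and Month 3 (Appendices 2 and 3); interim looks at 15 and 50 per group (13.5.2); 200 per arm (13.7).

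**Assumptions.** Constant background hazard h, equal in both arms, 1% to 10% per year; added risk e from reduction after the baseline; one-sided 0.05 at the interims (no level is stated) and two-sided 0.05 at the end. The gap g from screening to Day 0 is 90 days for everyone (worst case) or 45 days; g = 0 stands for a Day 0 baseline.

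**Share of background conversions that predate vaccination**, g/(g + t):
- Day 30: 90/120 = 75%; with a 45-day gap, 45/75 = 60%.
- Day 90: 90/180 = 50%; with a 45-day gap, 45/135 = 33%.

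**Expected number of such events**, n × (1 − exp(−h × 90/365.25)): per 50 participants, 0.12 at 1% and 1.2 at 10%; per 200, 0.49 and 4.9.

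**Event probabilities.** Control: p_c = 1 − exp(−h(g + t)/365.25). Reduction: p_r = 1 − (1 − p_c)(1 − e). The risk difference is (1 − p_c) × e.
- Day 30, e = 10 points, h = 10%: p_c is 0.0082 with a Day 0 baseline and 0.0323 with a 90-day-old one. The risk difference is 9.92 and 9.68 points.
- Day 90, e = 5 points, h = 10%: p_c is 0.0243 and 0.0481. The risk difference is 4.88 and 4.76 points.
- The ratio moves more. At Day 90, with e = 5 points and h = 5%, it falls from 5.0 to 3.0.

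**Exact Fisher power** (sum of binomial probabilities over all tables that reject):

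| Background per year | 50 per group, Day 30, 10-point excess: g = 0 / 45 / 90 | 200 per arm, Day 90, 5-point excess: g = 0 / 45 / 90 |
|---|---|---|
| 1% | 0.562 / 0.552 / 0.542 | 0.881 / 0.853 / 0.826 |
| 2% | 0.555 / 0.536 / 0.519 | 0.826 / 0.775 / 0.730 |
| 5% | 0.536 / 0.496 / 0.465 | 0.691 / 0.612 / 0.549 |
| 10% | 0.509 / 0.448 / 0.406 | 0.549 / 0.452 / 0.382 |

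DSA is kidney only and the kidney share is not given. At 100 per arm the Day 90 power falls from 0.36 to 0.34 (1%) or from 0.24 to 0.18 (10%). At 15 per group with a 20-point excess it stays near 0.35 (1%) or falls from 0.34 to 0.31 (10%). Keeping Day 0 positives in the denominator as non-events lowers the g = 0 column by at most about 0.02.

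**Sensitivity of the interim looks to one event** (one-sided p):
- 50 per group: 5 v 0 gives 0.028; 5 v 1 gives 0.10; with one control event, seven are needed (7 v 1, 0.030).
- 15 per group: 4 v 0 gives 0.0498; 4 v 1 gives 0.16; six are then needed (6 v 1, 0.040).

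A conversion before the intervention in the reduction group pushes the other way and could create a false signal.

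**The case against.** A reader might infer that the window hides an excess caused by reduction, or biases the comparison toward safety. The documents do not support that. Participants are randomized (13.3), and the screening window and the Week 4 and Month 3 tests are the same in both arms, so earlier conversions are equal in expectation. Reduction needs five days between randomization and vaccination, which could lengthen the gap slightly in that arm; even at 10% per year that adds only 0.10 × 5/365.25 = 0.14 points. The plan tests proportions and estimates no ratio, and the risk difference barely moves. A large excess remains visible: at 50 per group with a 90-day-old baseline, power for a 20-point excess is 0.88 to 0.97.

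A tempting illustration is that a doubled hazard would appear as (90 + 2 × 30)/120 = 1.25 at Day 30. The arithmetic is right, but the interim looks cannot detect a doubling with either baseline. At 50 per group, power is about 0.01 or less at every rate considered. Their size is the main limit, above all at 15 per group.

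Ninety days is also a maximum. Excluding past DSA and recent rejection may keep the background rate low, and at 1% to 2% per year the interim loss is only 2 to 4 percentage points. A figure in 13.5.2 is not shown, so guidance on reading the interim result may exist there.

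All of this limits the size of the problem. It does not supply a reference sample or make individual cases attributable. One further caution stands: Day 0 is five days into reduction in one arm, so counting only Day 0-negative cases could remove genuine reduction-period events from that arm alone.

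**Conclusion.** The point holds as a loss of precision and of attribution, not as a directional bias. In kidney recipients, the de novo count in both arms includes antibody that arose before the intervention.

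Under the assumptions above, the worst-case power loss at the 50-per-group look is 2 percentage points at 1% per year and 10 at 10%. At 200 per arm by Day 90 it is 5 to 6 points at 1%, about 10 at 2% and 17 at 10%. A 45-day gap costs a little over half as much.

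The results depend on a background rate that the documents do not give, on every sample being at the limit, and on assumed significance levels. The interim test counts Class II only, so its relevant background is lower than for all DSA. The change is worth making because the blood is already drawn and these comparisons carry the trial's claim about sensitization.

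**What to change.** In sections 8.7, 13.2 and 13.5.2:

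1. State the day from which the 90-day window is counted.
2. Reserve an aliquot of Day 0 research serum. Have the core HLA lab test it for any participant first DSA-positive at Week 4 or Month 3.
3. At each interim look and in the final analysis, report two counts by arm with the same Fisher test: all first positives, which is the count now planned, and those negative at Day 0. The second stands beside the first and does not replace it.
4. List Day 0 positives by arm, noting that Day 0 is five days into reduction in that arm. No reduction-arm event then drops out of what the DSMB sees.

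The cost is a handful of reflex assays, one reserved aliquot per kidney recipient and a short delay before each interim table. There is no extra visit or draw, provided the Day 0 volume is enough for HLA testing; the documents do not say. Day 0 serum cannot separate conversions before Day -5 from those in the first five days of reduction, and Appendix 3 marks no laboratory draw at Day -5. That is why both counts are needed.
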